2 STUDY RATIONALE

This pilot study seeks to establish that selective blockade of the CCR5/CCL5 axis as well as the potential anti-viral properties of Maraviroc may reduce disease severity. This proof-of-concept effort seeks to correlate differences in clinical outcomes to differential cytokine expression in the setting of CCR5 antagonism in patients infected with SARS-CoV-2. Maraviroc is FDA-approved for the treatment of CCR5-tropic HIV-1 and has a well-documented safety and tolerability record in previous trials in immunocompromised HIV patients. Maraviroc was not shown to have significant effect on the QT segment, can be delivered via oral formulation, and can be delivered safely to both patients with end-stage renal disease and dependence on hemodialysis 12. For these reasons, Maraviroc is an ideal candidate to study as a potential therapy for hospitalized patients with moderate-to-severe COVID-19.

3.2 Secondary Objectives

The secondary objective is to investigate the relationship between reduction of inflammatory markers (such as IL-6, CCL5, etc.) and clinical outcomes, including avoidance of respiratory decompensation and death.

4 STUDY DESIGN

4.1 Study Overview

This is a single-center, single-arm, open-label trial. Sixteen hospitalized patients will be enrolled. Screening data will be reviewed to determine subject eligibility. Subjects who meet all inclusion criteria and none of the exclusion criteria will be approached for consent prior to entering the study. Each subject will receive 7 days of Maraviroc twice daily. Each subject will have blood samples checked at time of enrollment (Day 0), Day 3, Day 7, and Day 15 or time of live discharge (whichever comes first) of the study. The total duration of subject participation will be five weeks. The total duration of the study is expected to be 16 weeks.

5 CRITERIA FOR EVALUATION

5.1 Primary Endpoint

This proof-of-concept trial will evaluate safety and tolerability of Maraviroc in SARS-CoV-2 infected patients. The primary endpoint is rate of patients who complete the 7-day course of Maraviroc without discontinuation for adverse events, hospitalization, or death. Additional endpoints include the percent of study population reaching clinical improvement, defined as time from enrollment to an improvement of two points on a seven-category ordinal scale (defined below), at Day 7.

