	 the patient or the quality of the data. This includes, but is not limited to, recent myocardial infarction in past 6 months, neurological, psychiatric, endocrine, or neoplastic diseases that are judged to interfere with participation in the study. Subjects with known diagnosis of human immunodeficiency virus infection (HIV) Subjects enrolled in another interventional trial (including one for COVID-19) that excludes participation in other trials or includes a potent CYP3A inhibitor or inducer (e.g. lopinavir-ritonavir). Subjects with ESRD or severe renal failure who are taking potent (moderate or strong) CYP3A inhibitors or inducers
TEST PRODUCT, DOSE, AND ROUTE OF ADMINISTRATION	Maraviroc will be administered orally twice daily for seven days.
DURATION OF SUBJECT PARTICIPATION AND DURATION OF STUDY	Subjects will be on study for up to 35 days Treatment: 7 days Follow-up: 28 days The total duration of the study is expected to be 4 months. 2 months for subject recruitment, 1 for final subject follow-up and 1 month for data run-off and analysis.
CONCOMMITANT MEDICATIONS	Prohibited: Lopinavir-Tenofovir Hydroxychloroquine Ivermectin
EFFICACY EVALUATIONS	
PRIMARY ENDPOINT	• In this proof-of-concept trial, the study team is chiefly concerned with safety and tolerability of Maraviroc in subjects diagnosed with SARS-CoV-2. The primary endpoint is rate of subjects who complete the 7-day course of Maraviroc without discontinuation for serious adverse event or death. Additional endpoints include the percent of study population reaching clinical improvement, defined as time from enrollment to an improvement of two points on a seven-category ordinal scale (defined below), at Day 7.
SECONDARY ENDPOINTS	Time to improvement to Score of 2 or less (Days) based on Ordinal scale: 1, not hospitalized with resumption of normal activities; 2, not hospitalized, but unable to resume normal

Version #: 2.8 Version Date: 11/6/2020 Page 3 of 30

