11 ADVERSE EXPERIENCE REPORTING AND DOCUMENTATION

11.1 Adverse Events

An adverse event (AE) is any untoward medical occurrence in a clinical investigation of a patient administered a pharmaceutical product and does not necessarily have a causal relationship with the treatment. An AE is therefore any unfavorable and unintended sign (including an abnormal laboratory finding), symptom or disease temporally associated with the administration of an investigational product, whether or not it is related to that investigational product. An unexpected AE is one of a type not identified in nature, severity, or frequency in the current Investigator's Brochure or of greater severity or frequency than expected based on the information in the Investigator's Brochure.

The study team will probe, via discussion with the subject, for the occurrence of AEs during each subject encounter and record the information in the site's source documents. Adverse events will be recorded in the patient case-report form. Adverse events will be described by duration (start and stop dates and times), severity, outcome, treatment, and relation to study drug, or if unrelated, the cause.

AE Severity

The National Cancer Institute's Common Terminology Criteria for Adverse Events (CTCAE) Version 4.0 should be used to assess and grade AE severity, including laboratory abnormalities judged to be clinically significant. Only for the specific Adverse Event of change in liver enzymes will The National Cancer Institute's Common Terminology Criteria for Adverse Events (CTCAE) Version 5.0 be used. If the experience is not covered in the modified criteria, the guidelines shown in Table 2 below should be used to grade severity. It should be pointed out that the term "severe" is a measure of intensity and that a severe AE is not necessarily serious.

Version #: 2.8 Version Date: 11/6/2020 Page 20 of 30

Table 2. AE Severity Grading

Severity (Toxicity Grade)	Description
Mild (1)	Transient or mild discomfort; no limitation in activity; no medical intervention or therapy required. The subject may be aware of the sign or symptom but tolerates it reasonably well.
Moderate (2)	Mild to moderate limitation in activity, no or minimal medical intervention/therapy required.
Severe (3)	Marked limitation in activity, medical intervention/therapy required, hospitalizations possible.

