12 DISCONTINUATION AND REPLACEMENT OF SUBJECTS

12.1 Early Discontinuation of Study Drug

A subject may be discontinued from study treatment at any time if the subject or the investigator feels that it is not in the subject's best interest to continue. The following is a list of possible reasons for study treatment discontinuation:

- Subject withdrawal of consent (or assent)
- Subject is not compliant with study procedures
- Adverse event that in the opinion of the investigator would be in the best interest of the subject to discontinue study treatment, including stoppage criteria for orthostatic hypotension
- Protocol violation requiring discontinuation of study treatment
- Drug supplier (Pfizer) request for early termination of study, after which study drug cannot be reasonably provided to subjects at no cost to them
- Positive pregnancy test (females)
- Pursuit of comfort measures only, inpatient hospice referral or transfer to inpatient hospice facility

Version #: 2.8 Version Date: 11/6/2020 Page 22 of 30

If a subject is withdrawn from treatment due to an adverse event, the subject will be followed and treated by the study team until the abnormal parameter or symptom has resolved or stabilized.

Subjects who are discharged from the hospital will not continue taking Maraviroc outside the hospital. Early completion prior to seven days of therapy will not be considered early withdrawal from the study. All subjects who discontinue study treatment will undergo an early discontinuation visit as soon as possible and will be encouraged to complete all remaining scheduled research labwork (except in the instance of comfort measures and hospice). Subjects are free to withdraw from participation at any time, for any reason, specified or unspecified, and without prejudice.

Reasonable attempts will be made by the investigator to provide a reason for subject withdrawals. The reason for the subject's withdrawal from the study will be specified in the subject's source documents.

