12.4 Replacement of Subjects

Subjects who withdraw from the study treatment will not be replaced. Subjects who are discharged from the hospital due to clinical improvement prior to completing the 7-day course will not be replaced. Subjects may be added to the study to replace subjects with incomplete data (said subjects will continue to receive Maraviroc) stemming from research bloodwork processing errors due to mishandling of shipments resulting in compromised fidelity of samples.

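### The synopsis and Section 5.1 define the primary endpoint differently, and nothing in the plan says how to score a live discharge before Day 7

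*Combined protocol and SAP*

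**What the plan says.** The primary endpoint is stated twice in the current version 2.8 text.

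- Synopsis, Primary Endpoint: "rate of subjects who complete the 7-day course of Maraviroc without discontinuation for serious adverse event or death".
- Section 5.1: "rate of patients who complete the 7-day course of Maraviroc without discontinuation for adverse events, hospitalization, or death".

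Both places treat improvement on the ordinal scale at Day 7 as an additional endpoint, so this rate is the only primary one.

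Four other places bear on how it is scored.

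- Section 12.1 ends treatment at discharge: "Subjects who are discharged from the hospital will not continue taking Maraviroc outside the hospital". Its next sentence is "Early completion prior to seven days of therapy will not be considered early withdrawal from the study".
- Section 12.4 describes the same patients differently: "Subjects who are discharged from the hospital due to clinical improvement prior to completing the 7-day course will not be replaced".
- The Statistics entry of the synopsis lists a therapy-completion rate among the planned results, without defining completion.
- Section 12.1 allows drug to be stopped for an "Adverse event that in the opinion of the investigator would be in the best interest of the subject to discontinue study treatment". Seriousness is not required. Section 11.1 adds that "a severe AE is not necessarily serious".

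Section 15.3 plans frequencies and percentages for categorical data and gives no scoring rule. Section 15 promises a separate SAP, to be written before the final data are analysed.

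**The concern.** The two failure lists differ in substance. The synopsis counts serious adverse events; Section 5.1 counts any adverse event and adds hospitalization. A patient taken off drug for a non-serious event can therefore be classed differently depending on which page is followed.

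Separately, a patient who recovers and goes home on Day 4 cannot take seven days of drug, and neither definition says expressly how that patient is scored. If the answer is failure, faster recovery lowers the measured tolerability of the drug, which is the reverse of what a safety and tolerability endpoint should show.

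What is at stake is the headline result of a single-arm, open-label trial of 16. The promised SAP need only precede the final analysis. By then the investigators will know who stopped, why, and who went home early, so the definition could be settled with the results in view.

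**Working it through.** The plan gives no target rate, success threshold or expected completion rate, so there is no figure of its own to reproduce. The check is to score each type of patient under each reading and see what that does to the rate.

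**Two readings.** Literal: success means seven days of drug taken. For cause: failure means a stop for a reason on the list.

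| Patient | Literal, either list | For cause, synopsis | For cause, Section 5.1 |
|---|---|---|---|
| Takes all 7 days | success | success | success |
| Live discharge before Day 7 | failure | not a failure | not a failure |
| Stop for a non-serious adverse event | failure | not a failure | failure |
| Stop for a serious adverse event, or death | failure | failure | failure |
| Other stop (consent withdrawn, comfort measures or hospice) | failure | not a failure | not a failure |

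On the literal reading the lists do no work, because any incomplete course fails, and both definitions give one rate. The lists diverge only on the for-cause reading, and only for non-serious stops. Hospitalization separates no patients on either reading: all subjects are inpatients and drug ends at discharge, so a later readmission cannot be why it stopped.

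**Inputs.** n = 16 (Section 4.1), taking all 16 as dosed. The numbers of stops and early discharges are assumptions; the documents give no early-discharge share.

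**Formulas.** Rate = x/16. Exact (Clopper-Pearson) 95% limits: lower = Beta quantile(0.025; x, 16 − x + 1), upper = Beta quantile(0.975; x + 1, 16 − x), with upper = 100% when x = 16. One patient = 1/16 = 6.25 points.

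**For cause, one non-serious stop and nothing else.**
- Synopsis: 16/16 = 100% (79.4 to 100).
- Section 5.1: 15/16 = 93.75% (69.8 to 99.8).

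**For cause, one serious stop and two non-serious stops.**
- Synopsis: (16 − 1)/16 = 15/16 = 93.75% (69.8 to 99.8).
- Section 5.1: (16 − 1 − 2)/16 = 13/16 = 81.25% (54.4 to 96.0).

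**Literal, early discharges only.**
- 2 discharges: 14/16 = 87.5% (61.7 to 98.4).
- 8 discharges: 8/16 = 50% (24.7 to 75.3).
- For cause, the same patients give 16/16 = 100% (79.4 to 100).

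**The case against.** The best defence is that the literal reading is the plain one. Both definitions speak of completing the 7-day course, the synopsis lists a completion rate, and Section 12.4 describes early discharge as falling short of completion. The early-completion sentence in Section 12.1 concerns withdrawal from the study, not the endpoint. On that reading the difference between the lists has no numerical effect. This carries weight, but it does not settle the matter. It leaves the whole discontinuation clause redundant in both definitions, which suggests that the authors meant something narrower, and it makes fast recovery count against the drug.

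A second defence is that the trial is descriptive and reports adverse events by severity anyway. That stands, and it limits the severity of the point.

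A reader might also infer four stronger things that the documents do not support.

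- *That the two gaps add up.* They belong to alternative readings.
- *That Section 14.1 gives the chance of a discrepant stop.* Its discontinuation figures come from HIV trials in which treatment averaged 34 weeks (Section 14.3), against 7 days here. Its projection of less than one orthostatic discontinuation in 40 is said to be calculated in the same way as 6 to 8 cases of dizziness in 40. The stated dizziness rate gives 14.1/100 × 40 × 7/365 = about 0.1 events. No probability is offered here for that reason.
- *That the stopping reasons will be lost without a new CRF field.* Section 12.1 says only that "Reasonable attempts will be made by the investigator to provide a reason for subject withdrawals", and the discharge checklist in Section 10.11 has no such item. But the synopsis and Sections 14.1 and 14.3 already require discontinuations due to adverse events to be counted, and medication records are reviewed daily. A field would be convenient; it is not shown to be necessary.
- *That a wrong decision could follow.* There is no threshold to cross.

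**Conclusion.** The point holds. Two current definitions of the sole primary endpoint disagree, and the plan does not score early discharge. The same 16 patients can therefore yield different headline rates. The difference is 6.25 points per affected patient: between the lists for each non-serious stop on the for-cause reading, or between the readings for each early discharge. The figures of 87.5% and 50% rest wholly on assumed counts of 2 and 8 early discharges and show sensitivity, not expectation. All figures assume 16 dosed subjects.

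The harm is an ambiguous descriptive rate whose definition could be chosen after open-label outcomes are known. That makes it something the sponsor should fix, but it does not invalidate the trial.

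**What to change.** This concerns scoring only, not when drug is stopped. Amend the synopsis and Section 5.1 now, without waiting for the SAP:

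1. Use one failure definition in both places, for example discontinuation of Maraviroc for any adverse event, or death, during the planned 7-day course.
2. Remove hospitalization as a failure reason.
3. State that live discharge before Day 7 without such an event is not a tolerability failure.
4. Beside the primary rate, report the literal 7-day completion rate and the rate free of a stop for a serious adverse event or death, each with an exact 95% CI.
5. Tabulate all other stops by reason, including consent withdrawal and comfort measures or hospice. Otherwise a patient moved to hospice who dies after the 7 days would not appear as a failure anywhere but in the completion rate.

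The cost is a wording change in two places and two extra lines in the results. A CRF item for the reason drug stopped is optional. The drawback is that shortened courses count as tolerated; the literal completion rate discloses how many there were.

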5.2 Secondary Endpoints

- Time to clinical improvement, defined as time from enrollment to an improvement of two points on a seven-category ordinal scale (defined below) or live discharge from the hospital, whichever comes first
 - Ordinal scale: 1, not hospitalized with resumption of normal activities; 2, not hospitalized, but unable to resume normal activities OR hospitalized pending disposition, not requiring COVID-related care; 3, hospitalized, not requiring supplemental oxygen; 4, hospitalized, requiring supplemental oxygen; 5, hospitalized, requiring nasal high-flow oxygen therapy, noninvasive ventilation, or both; 6, hospitalized, requiring ECMO, invasive mechanical ventilation, or both; and, 7, death.
- Change in cytokine levels from time of enrollment to completion of therapy or live discharge from the hospital (whichever comes first)
- 7-, 14- and 28-day all-cause-mortality
- Time to improvement to Score of 2 or less (days)
- Days on mechanical ventilation

Version #: 2.8 Version Date: 11/6/2020 Page 10 of 30

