1 BACKGROUND

Severe Acute Respiratory Syndrome Coronavirus 2 (SARS-CoV-2) is the cause of Coronavirus disease 2019 (COVID-19) and was first reported in Wuhan, China in December 2019¹. Though a wide spectrum of clinical manifestations exists, patients often present with mild upper respiratory symptoms, progressing in some cases to a multifocal pneumonia with multiorgan compromise². As the natural history of SARS-CoV-2 is further understood, increased attention has been devoted to understanding disease progression and notably severe respiratory complications which are described as occurring after 7-14 days after the onset of illness. Initial retrospective studies of confirmed COVID-19 cases in tertiary hospitals in Hubei Province, China, revealed a range of 1-20 days for the progression of respiratory distress following illness onset^{1,2,3}. The clinical course of COVID-19 infections appears to have a high degree of heterogeneity, with some remaining relatively uncomplicated, some progressing to a moderate pneumonia, and others developing severe, progressive pneumonia characterized by dyspnea, tachypnea, and hypoxia. Increased levels of IL-6 and decreased levels of lymphocytes have been reported in severe illnesses in a retrospective cohort of patients from Jinyintan and Wuhan hospitals. Older age and common comorbidities including hypertension, diabetes, and coronary artery disease have been associated with increased mortality³.

In the negative randomized, controlled, open-label trial of Lopinavir-Ritonavir involving patients with COVID-19 and oxygen saturation of less than 94% on room air, 70% of patients required supplemental oxygen and 15% required high-flow nasal cannula or non-invasive mechanical ventilation on presentation. Only one patient required intubation on presentation, but 16% would eventually require mechanical ventilation during their hospitalization. At Day 7, only 6% of the subjects in the Lopinavir-Ritonavir reached clinical improvement of 2 points on a 7-point ordinal scale. At day 14, 45.5% of subjects reached 2-point clinical improvement, 15.2% of subjects had died, and 28% continued to require non-invasive and nasal cannula support. This early study highlighted the lengthy duration of hospitalization and late progression of respiratory failure in COVID-19.

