15.3 Analysis of Endpoints

Continuous data obtained will be expressed by mean ± standard deviation (SD) or interquartile range, as applicable. Categorical variables will be reported as frequency and percentages. ICU LOS (and mechanical ventilation LOS, respectively) will be regressed on available laboratory and biomarker data using multivariable linear regression. All analysis will be conducted in a professional statistical program. Mortality and percent of study population reaching clinical improvement at Day 7 will be compared to published results from Remdesivir for 5 or 10 Days in Patients with Severe COVID-19, and other available clinical trials including The Randomized Evaluation of COVID-19 therapy (RECOVERY) Trial.

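### Secondary outcomes lack a rule for death: time to improvement has no time-to-event method, and raw ventilator days and the length-of-stay regression score an early death as a good result

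*Combined protocol and SAP*

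**What the plan says.** Section 5.2 defines "Time to clinical improvement, defined as time from enrollment to an improvement of two points on a seven-category ordinal scale" or live discharge, whichever is earlier. It also lists time to reach a score of 2 or less, "7-, 14- and 28-day all-cause-mortality", and "Days on mechanical ventilation". It does not say what value a subject receives who dies or never improves.

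Section 15.3 is the only analysis text that could apply: "Continuous data obtained will be expressed by mean ± standard deviation (SD) or interquartile range, as applicable". The same section plans a multivariable linear regression of ICU stay and of ventilation stay on laboratory and biomarker data. Censoring, cumulative incidence, competing events and ventilator-free days appear nowhere.

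Section 15.1 includes eligible subjects with at least one dose, or with more than one serum sample set. Section 15 promises a detailed SAP before the final analysis, carrying any modifications. Section 3.2 makes the relation between falling inflammatory markers and clinical outcomes, including avoidance of death, the secondary objective.

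**The concern.** There are two separate problems, on different endpoints.

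First, a time to improvement exists only for someone who improves. Without a rule for the rest, a mean or an interquartile range describes improvers alone, and the figure can look short even when few subjects improve.

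Second, ventilator days are defined for everyone, but death ends the count. A subject who dies soon after intubation contributes a low number, which reads as a good result. The regression in section 15.3 uses stay lengths of this kind as its outcome. If adverse markers go with rapid death, those subjects enter with short stays. That can weaken or reverse the association that section 3.2 sets out to study.

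**Working it through.** The plan states no power, effect size or event count for these endpoints, so there is no figure of its own to reproduce.

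**1. How often the gap would matter (illustrative rates only).** N = 16 comes from section 4.1 ("Sixteen hospitalized patients will be enrolled"). The rates come from the lopinavir-ritonavir trial described in section 1: "At day 14, 45.5% of subjects reached 2-point clinical improvement, 15.2% of subjects had died", and 16% eventually ventilated. They are not assumptions of this trial.

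- Improved by Day 14: 16 × 0.455 = 7.3.
- Dead by Day 14: 16 × 0.152 = 2.4.
- Neither: 16 − 7.3 − 2.4 = 6.3.
- No improvement time by Day 14: 16 × (1 − 0.455) = 8.7, or 54.5%.
- P(at least one death by Day 14) = 1 − (1 − 0.152)^16 = 0.93.
- Ever ventilated: 16 × 0.16 = 2.6. P(at least one) = 1 − (1 − 0.16)^16 = 0.94.

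At such rates the median over all 16 is not reached by Day 14, because 45.5% is below 50%. A mean over those improved by Day 14 would use about 7 subjects and could not exceed 14 days.

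**2. Ventilator days (assumed durations).** Two of 16 are ventilated; the other 14 are never ventilated and survive to Day 28.

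| Scenario | Mean ventilator days, all 16 | Mean, ventilated only | Mean ventilator-free days to Day 28, death = 0 |
|---|---|---|---|
| One dies after 2 days, one extubated at 12 | (2 + 12)/16 = 0.88 | 14/2 = 7.0 | (14 × 28 + 0 + 16)/16 = 25.5 |
| Both survive with 12 days each | (12 + 12)/16 = 1.50 | 24/2 = 12.0 | (14 × 28 + 16 + 16)/16 = 26.5 |

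Raw days favour the scenario with the death. Ventilator-free days favour the scenario without it.

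**3. The regression.** Take the two ventilated subjects of the first scenario and suppose the one who dies has the higher marker level. Going from the lower to the higher marker, ventilation stay falls from 12 to 2 days, so the higher marker appears to go with a better course. On ventilator-free days the same pair falls from 16 to 0, so the higher marker goes with a worse course. The reading changes sign with the outcome definition alone.

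**The case against.** A reader might infer that the plan orders mean ± SD for these endpoints and drops deaths and non-improvers. The documents do not support that. Section 15.3 leaves the choice between mean ± SD and interquartile range open and names none of these endpoints. No section excludes anyone for lack of improvement, and section 15.1 takes in all eligible dosed subjects. A rank summary over all 16 with non-improvers placed last would be consistent with the text. Exclusion is an inference from silence.

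A reader might also take the section 1 rates as a benchmark and conclude that the true median exceeds 14 days. That would be a statement about another trial. The comparators named in section 15.3 are a remdesivir trial and RECOVERY, and section 1 describes its 45.5% only as two-point improvement, without the live-discharge alternative in section 5.2.

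The possible harm is also limited. This is a single-arm proof-of-concept trial, and the external comparisons planned are of mortality and of the percentage improved at Day 7. The latter has the whole study population as its denominator. Mortality at three time points is reported alongside, so deaths would not be hidden. The specified regression uses stay lengths, not time to improvement. The promised SAP could settle all of this.

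These limits stand, but they do not remove the point. A mean of improvement times still needs a value that no section supplies. Ventilator days and the stay-length regression are stated as they are, so that part needs no inference about exclusion. Separate mortality figures correct neither of them. The detailed SAP is not among the documents, so the current text is the default.

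**Conclusion.** The point holds in two parts. For the two time-to-improvement endpoints, the plan lacks a time-to-event method and a value for subjects who die or never improve; this is a gap, not a stated exclusion. For ventilator days and the stay-length regression, what is stated can itself put outcomes in the wrong order: 0.88 against 1.50 days in the example, where the lower figure belongs to the scenario with a death.

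The example rests on assumed durations and on two ventilated subjects. The expected counts rest on rates from another trial and show only that the situation is likely to arise with 16 subjects. The primary endpoint, mortality and the Day 7 improvement percentage are unaffected. The matter should be settled before outcomes are analysed, because the trial is open-label and small enough for one or two deaths to move these summaries.

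**What to change.** State the following in section 15.3 or in the promised SAP:

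- **Time to improvement (both definitions), all dosed subjects.** Report the cumulative incidence of improvement to Day 28 with death as a competing event, so that deaths stay in as never improved. Subjects alive and not improved are censored at Day 28, or at last contact if earlier. Give the median only if it is reached.
- **Ventilation.** Report ventilator-free days to Day 28, with death by Day 28 set to 0, beside raw ventilator days.
- **Biomarker regression.** Replace raw ICU and ventilation stay with a death-penalised outcome of the same kind (ICU-free and ventilator-free days to Day 28, death = 0).
- **Any use of the section 1 rates** should be labelled illustrative.

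No new data collection is needed. Daily ordinal scores (section 16.1), mortality to Day 28 (section 5.2) and follow-up to Day 35 (sections 10.12 and 10.13) are already planned. The cost is a few lines of text, a little more analysis work, and reported times that will look less favourable.
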